**3.3 EXCLUSION CRITERIA**

Subjects will be excluded if ANY of the following conditions apply:

General Exclusion Criteria:

1. Subject's estimated life expectancy is  $< 12$  months.
2. Subject has a history of transplanted kidney(s), has had another recent organ transplant or polycystic kidney disease.
3. Subject with estimated eGFR  $\leq 25\text{mL/min}/1.73\text{m}^2$
4. Subject has a history of bleeding diathesis or coagulopathy or refuses blood transfusions.
5. Subject has a known contraindication to heparin, aspirin, thienopyridine, other anti-coagulant/antithrombotic therapies, contrast media, stainless steel, and/or PTFE.
6. Subject has had a previous renal bypass operation, a bypass is planned, or the target lesion is located within or beyond a bypass graft.

7. Subject has received a thrombolytic agent within the past 30 days.
8. Subject has documented acute pulmonary edema or systolic heart failure with ejection fraction < 30% and/or hospitalization requiring intubation and ventilation support for this diagnosis within the previous 90 days or hypertensive emergencies defined as resulting in organ damage.
9. Concurrent enrollment in any investigational trial wherein subject's participation has not been completed.
10. Subject has had a planned or anticipated cardiovascular surgical or interventional procedure outside of the affected renal artery (including, but not limited to, aortic, renal, cardiac, carotid, femoro-popliteal, and below the knee) within 30 days prior to the index procedure and prior to completion of the 30 day follow-up.
11. Subject has suffered a stroke or Transient Ischemic Attack (TIA) in the past 3 months.
12. Subject is pregnant, lactating, or is of child-bearing potential and plans to become pregnant during the follow-up trial period.
13. Subject with significant valvular disease.
14. Subject with known significant proteinuria > 2+ or > 2.0gm/d.
15. Subject with known bilateral upper-extremity arterial stenosis that result in spuriously low arm pressures or without the ability to gain reliable blood pressure measurements in at least one upper extremity.
16. Subject with active sepsis.
17. Subject with serum creatinine  $\geq$  3.0mg/dL.
18. Subject with NYHA Class IV at the time of enrollment.
19. Subject is on hemodialysis.
20. Subject has a history of renal aneurysm.
21. Subject with cardiogenic shock.
22. Subject with cardiomyopathy.
23. Subject has an uncontrolled concurrent illness, including but not limited to ongoing or active infection or active autoimmune disease requiring immunosuppressive therapy.
24. Any subject with clinically significant cardiovascular, respiratory, neurologic, hepatic, endocrine, major systematic disease, making implementation or interpretation of the protocol or protocol results difficult or who in the opinion of the investigator would not be a good candidate for enrollment.

Anatomic Exclusion Criteria:

1. The planned site of intervention is totally occluded or has an anatomic configuration likely to prohibit adequate dilatation, and/or passage or implantation of the investigational device.
2. Subject has multiple ipsilateral lesions of the target renal artery that cannot be covered by a single stent.
3. There is a previously implanted stent in the target vessel or there is a previously implanted stent in the contralateral vessel < one year.

4. Subject has fibromuscular dysplasia, in renal artery and/or other vascular bed.
5. The target lesion site is associated with a thrombus.
6. Target lesion treated with laser atherectomy, directional atherectomy or other adjuncts to PTA.
7. Subject has a critical stenotic (> 70%) small accessory renal artery.
8. Subject has an abdominal aortic aneurysm > 4.0cm in diameter or a severe atherosclerotic aorta.
9. Main renal artery length  $\leq$  15mm precluding the safe deployment of a covered renal stent.
10. Any lesion that would include blocking of renal artery side branch.
11. Renal artery stenosis due to dissection of renal artery: spontaneous or traumatic.

### **3.4 SUBJECT SCREENING**

At each investigational site, a member of the trial research team will approach individual subjects (or their legal representative or guardian) who are potential candidates for participation. A trial research staff member will explain the purpose, procedures, device, and intent of the trial to each potential participant. Interested subjects will be invited to join the trial and asked to provide written informed consent prior to initiation of any trial related procedure.

A focused hypertension medical history will be reviewed and recorded for each subject. History should capture at least three months' information prior to screening to document that reasonable and aggressive efforts were previously made to manage hypertension via a broad variety of medications that have been tried and failed. Potential subjects will have been on a stable medication regimen for a minimum of two weeks prior to beginning the Medical Documentation Screening period. A minimum of a 14-day Medical Documentation Screening period is required to refine case selection and identify subjects most likely to benefit from renal revascularization\*. Titration of the subject's antihypertensive medications will not be allowed during this period. The Medical Documentation Screening period will proceed in the following sequence:

1. Potential subjects will complete an initial office visit during which 3 blood pressure measurements will be obtained, utilizing a standardized technique (APPENDIX 3: METHODOLOGY FOR OFFICE-BASED BP MEASUREMENT), to determine an average SBP value. If the average initial SBP value for this visit is  $\geq$  150mmHg, then the subject will proceed to step 2.
2. The subject will be tested for proteinuria, have labs drawn, can be scheduled for the procedure, and will proceed to step 3.
  - Throughout the Medical Documentation Screening period, subjects will complete

a daily questionnaire every day until the day of procedure that will ask if the subject is taking blood pressure medications as prescribed.

- If the subject has recorded daily medication compliance via the completed questionnaire, the subject proceeds to step 3.

[figure not shown]
3. Subjects will have their BP taken in the office every two weeks prior to the scheduled procedure. Only subjects with an average SBP value  $\geq 150$  mmHg at this visit after 3 sequential blood pressure measurements are taken, utilizing a standardized technique (APPENDIX 3: METHODOLOGY FOR OFFICE-BASED BP MEASUREMENT), will be allowed to proceed.

- A minimum of two office visits are required within the 14 day Medical Documentation Screening period. If the procedure is scheduled for more than 14 days from the first visit, subjects should return every two weeks (+/- 3 days) for BP assessment and monitoring and the daily questionnaire for medication compliance should be continued until the day of procedure.

4. On the day of the scheduled procedure, or no more than 14 days prior, 3 sequential blood pressure measurements will be taken again, utilizing a standardized technique (APPENDIX 3: METHODOLOGY FOR OFFICE-BASED BP MEASUREMENT), to determine an average SBP value. Only subjects with an average SBP of  $\geq 155$  mmHg from the three measurements taken on the last day of the 14-day Medical Documentation Screening period will be considered for enrollment.

\*NOTE: If a subject is seen in the clinic with a medical history documenting at least a 1 month stable medication of  $\geq$  three anti-hypertensive medications from at least three classes of drugs, one of which being a diuretic and documented SBP  $\geq 155$  mmHg, they will be allowed to skip the formal Medical Documentation Screening period and to be enrolled as soon as the history and baseline labs are reviewed by the Medical Monitor. Subjects must complete the daily questionnaire from the day of consent through the day of procedure. All other protocol requirements that would have normally occurred during the two week screening period must still be completed even if the screening period is skipped. These assessments include: vitals, BP, Labs, test for proteinuria, physical exam, and a pregnancy test and would need to be completed either on the day of consent or prior to the day of procedure.

**Figure 1: Medical Documentation Screening Period Flow Diagram**

### **3.5 SUBJECT ENROLLMENT**

Up to 138 subjects will be enrolled in this clinical trial. Eligible subjects will be enrolled consecutively at each investigational site. A patient is deemed enrolled into the trial once all inclusion criteria have been met and reviewed by an independent medical monitor, no exclusion criteria exist, the operator determines the target lesion is  $\geq 80\%$  diameter stenosis or FFR  $< 0.8$  and the trial device enters the subject. The screening log will then be completed to document the enrollment, subject number, or reason for non-enrollment of subjects screened but not enrolled in the ARTISAN trial.

### **3.6 SUBJECT DISCONTINUATION**

Each enrolled subject shall remain in the trial until completion of the required follow-up period, however, a subject's participation in any clinical trial is voluntary and the subject has the right to withdraw at any time without penalty or loss of standard of care treatment. Conceivable reasons for discontinuation may include, but not be limited to, the following:

1. Subject death
2. Subject voluntary withdrawal
3. Subject withdrawal by physician as clinically indicated

The reason for subject discontinuation must be documented on the electronic Case Report Form (eCRF) and source documents. Investigators must also report all subject discontinuations to their IRB/EC as defined by their Institution's procedure.

### **3.7 SUBJECT WITHDRAWAL**

All subjects should be encouraged to remain in the trial throughout the entire follow up time period. If a subject decides to discontinue trial participation, the reason for their discontinuation must be recorded in the medical record and submitted via the eCRF. Subjects who discontinue participation prematurely will be included in the analysis results if the 9-month visit has been reached.

### **3.8 EARLY TERMINATION OF THE TRIAL**

Possible reasons for early trial termination include:

1. Unanticipated Adverse Device Effects (UADEs) present an unreasonable risk to subjects.
2. The Data Safety Monitoring Board (DSMB) makes a decision for the early termination of the trial per recommendation (refer to Section 7.1).

[figure not shown]
If the trial is terminated early, Atrium will provide a written statement to the Investigator to enable notification to their IRB/EC.

## 4.0 PROCEDURES AND ASSESSMENTS

A table summarizing the study procedures is presented in APPENDIX 4: SCHEDULE OF EVENTS. A summary of the assessments to be performed at each interval is presented below.

The following diagram summarizes the timing of visits in this trial:

**Figure 2: Trial Flow Diagram**

#### **4.1 SCREENING PROCEDURES**

At each investigational site, a member of the trial research team will approach individual subjects (or their legal representative) who are potential candidates for participation. A trial research staff member will explain the purpose, procedures, device, and intent of the trial to each potential participant. Interested subjects will be invited to join the trial and asked to provide written informed consent prior to initiation of any trial related procedure.

##### **4.1.1 DAY -14: INITIAL MEDICAL DOCUMENTATION SCREENING VISIT**

Trial subjects will complete an initial office visit. The assessment will consist of:

- Signed ICF
- Inclusion/exclusion criteria
- Demographics
- Collection of medical history
- Collection of focused anti-hypertensive medical history
- Height/weight
- Vital signs
- Collection of BP (following the methodology for measurement as outlined in APPENDIX 3: METHODOLOGY FOR OFFICE-BASED BP MEASUREMENT)
- Laboratory assessments
  - Chem12 Panel which includes: Glucose, Calcium, Albumin, Total protein, Sodium, Potassium, CO2, Chloride, BUN, creatinine, ALP, ALT, AST, and bilirubin.
  - Test for proteinuria. Urine proteinuria may be tested by dipstick. A level of > 2+ is exclusionary unless a 24 hour urine shows that the urinary protein is < 2gm/d.
- Physical exam
- Female subjects of childbearing potential will have a pregnancy test
- Documented clinical evidence to support likelihood of angiographic findings > 80% whether it is DUS, CTa, MRa or other medical evidence
- Collection of concomitant medications

##### **4.1.2 DAY -7: MEDICAL DOCUMENTATION SCREENING VISIT(S)**

Trial subjects will return to the office every 2 weeks prior to the scheduled procedure to monitor their BP. Assessments will consist of:

- Collection of BP (following the methodology for measurement as outlined in APPENDIX 3: METHODOLOGY FOR OFFICE-BASED BP MEASUREMENT)
- Collection of concomitant medications
- Collection of AEs, if applicable

#### **4.2 PRIOR TO THE PROCEDURE**

The following tests and examinations must be performed prior to the procedure to verify eligibility.

##### **4.2.1 DAY 0: DAY OF PROCEDURE**

Trial subjects will return to the office the day of the scheduled procedure. Assessments will consist of:

- Inclusion/exclusion criteria
- Vital signs
- Collection of BP (following the methodology for measurement as outlined in APPENDIX 3: METHODOLOGY FOR OFFICE-BASED BP MEASUREMENT)
- Laboratory assessments
  - Chem12 Panel
- Physical exam
- Female subjects of childbearing potential will have a pregnancy test
- Collection of concomitant medications
- Collection of AEs, if applicable
- Begin dual anti-platelet therapy (aspirin plus thienopyridine) pre-procedure as required per Table 2: Concomitant Medications

##### **4.2.2 DAY 0: ANGIOGRAPHY**

Angiography is to be performed according to standard hospital procedure for renal stent implantation and in compliance with procedures outlined in the Angiographic Core Laboratory Manual of Operations.

#### **4.3 STENT IMPLANTATION**

Implantation of the iCAST™ RX Stent System should be performed according to the IFU provided with the investigational device. Refer to the manufacturer's IFU for instructions including: sizing and selection of the stent, preparation of the stent and delivery catheter, introduction and positioning of the stent, deployment of the stent, removal of an unexpanded stent, and emergency withdrawal of an expanded stent.

- Administer IV heparin, low molecular weight heparin, or bivalirudin per routine hospital practice. Target Activated Clotting Time (ACT) must be >250 seconds prior to implantation of the iCAST™ RX Stent System if heparin or low molecular weight heparin is administered. Bivalirudin should be administered in line with the prescribing information according to the weight of the patient.
- NOTE: Pre-dilatation of the lesion and the use of distal protection filters will be at the Investigators discretion and are not distinctly prohibited nor required.

#### **4.4 IMMEDIATE POST-PROCEDURE**

Post-procedure, subjects should continue dual anti-platelet therapy (aspirin plus thienopyridine) for a minimum of 3 months except when it is medically necessary to take subjects off therapy.

- Collection of AEs, if applicable

#### **4.5 POST PROCEDURE FOLLOW-UP EVALUATIONS**

All trial subjects will be followed through hospital discharge and will undergo follow-up evaluations for a total of 36 months at the following time points:

##### **4.5.1 DAY 30 (+14/-7 DAYS): FOLLOW-UP VISIT**

Trial subject follow-up clinic evaluation must occur 30 days post-procedure. The assessment will consist of:

- Vital signs
- Collection of BP (following the methodology for measurement as outlined in APPENDIX 3: METHODOLOGY FOR OFFICE-BASED BP MEASUREMENT)
- Laboratory assessments
  - Chem12 Panel
- Physical exam
- DUS
- Collection of concomitant medications
- Collection of AEs, if applicable
- Subjects remain on dual anti-platelet therapy as required per Table 2: Concomitant Medications

##### **4.5.2 6-MONTH (+/-30 DAYS) PHONE CALL**

Trial subject follow-up telephone evaluation must occur 6 months post-procedure. The assessment will consist of:

- Collection of concomitant medications
- Collection of AEs, if applicable

##### **4.5.3 9-MONTH (+/- 30 DAYS) FOLLOW-UP VISIT**

Trial subject follow-up clinic evaluation must occur 9 months post-procedure. The assessment will consist of:

- Vital signs
- Collection of BP (following the methodology for measurement as outlined in APPENDIX 3: METHODOLOGY FOR OFFICE-BASED BP MEASUREMENT)
- Laboratory assessments
  - Chem12 Panel
- Physical exam
- DUS\*
- \*Angiography if DUS indicates  $\geq 60\%$  stenosis
- Collection of concomitant medications
- Collection of AEs, if applicable

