## 5.2 SAMPLE SIZE

For a one-sided alpha of 0.025 and desired power of 87%, sample size for the primary patency endpoint is established by assuming a hypothesized primary patency incidence of 0.82, which gives 125 evaluable subjects therefore, accounting for 10% attrition, 138 subjects are needed for this endpoint. At the proposed evaluable sample size of 125, no more than 27 subjects (22%) can fail primary patency in order to meet the endpoint hypothesis.

For the endpoint of reduction in SBP, we assume an average reduction of 13.7mmHg. Under a hypothesized standard deviation of 12mmHg for a difference in SBP there will be 92% power to meet the Performance Goal. This standard deviation is conservatively approximated based on the expected range of SBP at baseline of 155mmHg to 180mmHg divided by 3 and assuming a similar standard deviation at the 9-month follow up. A mean difference in SBP at 9-months of 12mmHg will be required in order to reject the null hypothesis at a one-sided alpha of 0.025 at the proposed sample size.

The primary endpoints of primary patency and reduction in SBP are powered at 87% and 92%, respectively, in order to maintain the overall trial power at 80% to meet both endpoints.

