5.5 Determination of Sample Size

For a one-sided alpha of 0.025 and desired power of 87%, sample size for the primary patency endpoint is established by assuming a hypothesized primary patency incidence of 0.82, which

Amendment #1: 15Jul13

gives 125 evaluable subjects therefore, accounting for 10% attrition, 138 subjects are needed for this endpoint. At the proposed evaluable sample size of 125, no more than 27 subjects (22%) can fail primary patency in order to meet the endpoint hypothesis.

For the endpoint of reduction in SBP, we assume an average reduction of 13.7mmHg. Under a hypothesized standard deviation of 12mmHg for a difference in SBP there will be 92% power to meet the Performance Goal. This standard deviation is conservatively approximated based on the expected range of SBP at baseline of 155mmHg to 180mmHg divided by 3 and assuming a similar standard deviation at the 9-month follow up. A mean difference in SBP at 9-months of 12mmHg will be required in order to reject the null hypothesis at a one-sided alpha of 0.025 at the proposed sample size.

The primary endpoints of primary patency and reduction in SBP are powered at 87% and 92%, respectively, in order to maintain the overall trial power at 80% to meet both endpoints.

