7.6 Endpoints, Safety Outcomes and Other Parameters

7.6.1.Primary Endpoints

Primary Patency Rate

In order to mitigate the challenges with DUS interpretation, clinical validation through independent noninvasive core laboratory and/or angiography will be performed in order to correctly validate and definitively assess percent diameter stenosis. DUS is highly reliable in identifying widely patent stents – however, correlation studies of DUS with angiography have confirmed that DUS is not as accurate when results suggest a stenosis. To lessen the risk of inaccurate readings, if a stenosis is detected in DUS (RAS > 60%) or if the DUS is non-diagnostic due to an imaging quality problem then a contrast angiogram will be used to assess the degree of restenosis of the covered stent(s) at the 9-month visit (± 30 days).

The primary efficacy variable is the primary patency rate, defined as continuous patency without the occurrence of a total occlusion (complete obstruction or a closure of a passageway or vessel determined by DUS or contrast angiogram) of the original lesion, and

Amendment #1: 15Jul13

Confidential

- without a re-intervention due to a clinically driven restenosis or occlusion to treat a partial or total occlusion of the stented segment,
- or bypass of the stented segment due to clinically-driven restenosis or occlusion

The primary patency will be calculated on a per lesion basis – for purpose of analysis in cases in which multiple lesions are covered by one stent then the stented segment will be considered as one lesion. The cumulative incidence of patency at 9 months will be computed as the number of lesions that met primary patency divided by the number of subject-lesions for the population being analyzed.

Change from Baseline in Systolic Blood Pressure

Systolic blood pressure will be assessed at each follow-up study visit. Blood pressure measurements will be obtained with a certified, calibrated, and validated equipment. Subjects will be instructed to refrain from exercise, smoking or caffeine ingestion for 30 minutes before blood pressure measurement, and measurements will be obtained after at least 5 minutes of rest. At each time point, a minimum of three (3) readings separated by 2 minutes will be averaged.

The primary clinical outcome is the improvement in systolic blood pressure (SBP) at 9-months as compared to baseline systolic blood pressure computed as follows:

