8.3 Handling of Dropouts or Missing Data

Due to the early termination of study enrollment missing data will not be imputed as there is no need to assess the robustness of the primary analysis by evaluating the impact of missing data.

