9.9.1. Primary Patency Analysis

The primary endpoint will be the cumulative incidence of primary patency at 9-months of study computed as the number of subjects with primary patency at 9-months divided by the number of subjects in the ITT population. An exact binomial one-sided 95% confidence interval will be constructed and the upper limit compared to the Performance Goal equal to 70%. A p-value for the one-sided exact test of the difference between the observed rate and the Performance Goal will be presented. The primary analysis will be analyzed with observed data only.

A planned subgroup analysis of the primary functional endpoint will be performed (details are provided in section 9.9.4

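### SAP 9.9.1 divides by the whole ITT population yet uses observed data only, so the 9-month patency rate has two possible denominators

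*Protocol*

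**What the plan says.** **The rate.** SAP 9.9.1 takes the number of subjects with primary patency at 9 months "divided by the number of subjects in the ITT population". SAP 9.3 defines that population as everyone enrolled. The same paragraph of 9.9.1 adds: "The primary analysis will be analyzed with observed data only".

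**The unit.** SAP 7.6.1 counts patent lesions "divided by the number of subject-lesions for the population being analyzed", and SAP 8.8 names the lesion as the unit of analysis for this endpoint.

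**The 9-month reading.** Status comes from duplex ultrasound, with angiography as back-up. The visit list in protocol 4.5.3 gives the back-up in short form: "Angiography if DUS indicates" at least 60% stenosis.

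**Missing data.** SAP 8.3 says "missing data will not be imputed as there is no need to assess the robustness of the primary analysis". SAP 2 and 6.2 also exclude imputation. Protocol 5.3.3 and 5.3.6.1 had planned a tipping-point analysis over all combinations of success and failure for the missing cases. The SAP removes it and says so.

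**Early discontinuation.** Protocol 3.7: "Subjects who discontinue participation prematurely will be included in the analysis results if the 9-month visit has been reached".

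**Sample size.** Protocol 5.2 works with evaluable subjects: "At the proposed evaluable sample size of 125, no more than 27 subjects (22%) can fail primary patency". SAP 5.5 repeats the calculation, which "gives 125 evaluable subjects therefore, accounting for 10% attrition, 138 subjects are needed".

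**Status of the result.** SAP 6.1 records that enrolment ended at 68 subjects. SAP 2 and 6.2 make all inference descriptive.

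**The concern.** Some lesions may have no 9-month patency status, whether from a missed visit, a withdrawal or a scan that was never resolved. For such a lesion the two instructions in SAP 9.9.1 diverge. Under the written fraction it stays in the denominator and can never enter the numerator, so it is scored as a failure. Under the observed-data sentence it drops out of both. The two readings give different rates from identical data, and the one that follows the formula literally imputes failure in a plan that forbids imputation.

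The unit is a second conflict in the same formula: 9.9.1 counts subjects where 7.6.1 and 8.8 require lesions.

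At stake is the reported value of a co-primary endpoint, which SAP 9.9.1 still sets beside a 70% performance goal with a confidence limit and a p-value. The tipping-point analysis would have displayed both extremes. Without it, a reader of the report may not know which denominator was used. The systolic blood pressure co-primary is not affected.

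**Working it through.** **1. The plan's own figure.** Inputs from protocol 5.2 and 5.1: 125 evaluable, goal 0.70, assumed patency 0.82, one-sided alpha 0.025. At most 27 failures means at least 125 − 27 = 98 patent. Exact binomial:
- P(X ≥ 98 | n = 125, p = 0.70) = 0.0230
- P(X ≥ 97 | n = 125, p = 0.70) = 0.0368
- P(X ≥ 98 | n = 125, p = 0.82) = 0.876

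So 27 failures is the correct limit, and the power agrees with the stated 87%. The planning denominator was therefore cases with a known outcome, not all enrolled.

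**2. The two readings.** Let N be all ITT cases, u those with no 9-month status, and x those observed to be patent.
- Observed-data rate: x/(N − u)
- Written-denominator rate: x/N
- Gap: with p = x/(N − u), p − x/N = p·u/N

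At p = 0.82, each undetermined case moves the rate by 0.82/68 = 1.2 percentage points if N = 68, or 0.82/82 = 1.0 point if N = 82. N = 68 assumes one lesion per subject. N = 82 is 68 × 1.2 = 81.6, rounded; the 1.2 lesions per subject is quoted in protocol 2.1 from another trial. The actual lesion count is not in the documents.

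**3. Range.** The documents give no value for u. The shares below are assumptions. The 10% rows borrow the plan's attrition allowance, and observed patency is held near 0.82.

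| N | u (nominal share) | x/(N − u) | x/N | Gap (points) |
|---|---|---|---|---|
| 68 | 3 (5%) | 53/65 = 81.5% | 53/68 = 77.9% | 3.6 |
| 68 | 7 (10%) | 50/61 = 82.0% | 50/68 = 73.5% | 8.4 |
| 82 | 8 (10%) | 61/74 = 82.4% | 61/82 = 74.4% | 8.0 |
| 68 | 10 (15%) | 48/58 = 82.8% | 48/68 = 70.6% | 12.2 |

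If u = 0 the readings coincide.

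**4. Which reading the plan favours.** The observed-data sentence, the ban on imputation, protocol 3.7 and the evaluable-subject boundary all point to exclusion. The fractions written in 9.9.1 and 7.6.1 point the other way. No section of either document reconciles them.

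**5. Exclusion is not neutral if protocol 3.7 is applied as written.** A subject whose stent occludes at month 4 and who withdraws at month 6 has a known failure but never reaches the 9-month visit, so 3.7 removes that failure. In the 50/61 example there are 11 failures. Losing one of them this way gives 50/60 = 83.3%, which is 1.4 points higher. The removal can only raise the patency rate.

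**The case against.** The best defence is that 9.9.1 has one natural reading: it names the ITT population and then restricts it to those observed. Scoring an unread lesion as not patent would be failure imputation, which the SAP excludes in three places. In addition, SAP 7.2 refers the reader to the data management plan for how data are handled at the 9-month endpoint, and SAP 8.5 says the CEC Charter sets minimum data and a classification algorithm. Either may hold the rule; neither is among the documents. Finally, nothing confirmatory depends on the answer.

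Much of this stands. Exclusion is probably what was meant, and the consequence is limited. It does not remove the point: the fraction as printed contradicts the sentence that follows it, the unit is wrong by the SAP's own 8.8, and a descriptive rate still needs one denominator. The supportive time-to-event analysis in SAP 7.4 does not define this rate. The per-protocol sensitivity analysis takes the same form of denominator from 7.6.1.

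A reader might infer two stronger points that the documents do not support:

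- *That unreadable scans go unresolved.* Protocol 4.5.3 ("Angiography if DUS indicates" at least 60% stenosis) and footnote 5 of both schedules name no other trigger. But the protocol summary, protocol 3.0 and SAP 5.1 and 7.6.1 all require angiography after non-diagnostic ultrasound, and protocol 4.0 describes its visit lists as a summary. The full rule exists.
- *That the original 138-subject test was undermined.* Protocol 5.3.5.1 contains neither the divide-by-ITT wording nor the observed-data sentence, and the protocol kept the tipping-point analysis. Judging the abandoned design by a SAP sentence written for the curtailed trial sets up a comparison that neither document makes.

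**Conclusion.** The point holds as a minor internal conflict in the definition of a co-primary estimate. SAP 9.9.1 gives a denominator that, read literally, counts undetermined cases as not patent, against its own observed-data sentence and the no-imputation rule. It also uses subjects where the SAP elsewhere requires lesions.

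The size is 1.0 to 1.2 percentage points per undetermined case at a patency of 0.82. With 10% undetermined, the reported rate is about 82% or about 74%. That 10% is an assumption and should not be read as an expected figure: the true number is unknown and could be zero. Because enrolment stopped at 68, only a descriptive result is affected. The conclusion also depends on the data management plan and CEC Charter not already settling the matter.

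**What to change.** In SAP 9.9.1 and 7.6.1, replace the fraction with: *patent lesions divided by ITT lesions with a determined 9-month patency status; an occlusion, re-intervention or bypass that meets the failure definition at or before 9 months counts as determined, including in subjects who later withdraw.*

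State that, for this endpoint, the rule overrides the restriction in protocol 3.7 to subjects who reached the 9-month visit. SAP 6.2 is a natural place to list it. Report the number of undetermined lesions beside the rate. If the data management plan or CEC Charter already contains this rule, a cross-reference in 9.9.1 is enough.

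The cost is one sentence in each of two SAP sections, a line recording the departure from protocol 3.7, and one extra count in the patency table. No new data, procedure or protocol amendment is needed, and protocol 4.5.3 and the schedule footnotes can stay as they are.
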